C.1.2. Experience in using clinical lab methods to provide evidence for WP regulation. Our team has pioneered the use of clinical lab methods to the study of WP, and has applied them recently to the study the potential of tobacco flavor regulation for the WP ([name] 2009, [name] 2019, a). In preparation for this application, [name] and [name] conducted a proof-of-concept pilot study to test the potential effect of HWLs on the device on WP smokers' satisfaction, and exposure to toxins ([name] 2019, b). We recruited 30 WP smokers, who completed two, 45-minute ad libitum smoking sessions that differed by HWL undivided condition (with vs. without) in a crossover design study. Exhaled carbon monoxide (eCO) was measured before and after each smoking session, and participants completed questionnaires assessing their smoking experiences and perceptions. This pilot study showed that placing HWL on the WP device has the potential to reduce WP smoker's positive experiences, and exposures (e.g. eCO). For example, we found lower levels of eCO following smoking the WP fitted with HWL (17.8 ppm) compared with smoking WP without HWL (24.5 ppm; $P<0.05$) (Figure 6). We will build on this experience by conducting a larger, well-powered, theory-driven study with a comprehensive assessment of change in harm perception and intention to quit, dependence, oxidative stress in EBC, and puffing behavior among young WP smokers in Florida.

C.1.3. Experience in using communication approaches to disseminate research results and advocate for policy change. In the past 2 years, [name], [name], and [name] have been collaborating to produce several educational videos about the harmful and addictive profile of WP smoking targeting different audiences (TV Channel 6). These videos have been used by Tobacco Free Florida to increase WP smokers and nonsmokers' awareness about WP health

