Design and Setting. Utilizing clinical lab methods, this aim provides broad testing of the top 4 HWLs on a myriad of WP smokers' subjective and objective outcomes. *We will recruit 2 groups of WP smokers (124 each, total 248; age 18-29 yrs) based on their use frequency (beginners: started WP smoking in the past 6 months, but smoke WP less than weekly; established: smoked at least once a week in the past 6 months) for a 2x2x2x4 within-subject (2: HWL vs no-HWL x 2: pre- vs post- smoking) and between-subject (2: beginner vs established smokers x 4: HWLs) experimental study. Participant in each group (beginner, established smoker) will be randomly assigned to one of the 4 HWLs conditions, and undergo 2 WP smoking sessions that differ by HWL on the WP device (HWL vs. no-HWL), with pre-/post-smoking assessment of harm perception, intention to quit, puffing behavior, satisfaction, urge to smoke, and toxicant exposure (CO, nicotine, oxidative stress) (Figure 9). We will use Latin Square crossover design balanced for carry-over effect (random order of 4 HWL condition), and to ensure equal distribution of study participants across gender. Accordingly, every subject will undergo 2 WP smoking sessions in the clinical lab setting differing by label (HWL vs. no-HWL) in a balanced random sequence; the same number of subjects gets each label and its order (1st or 2nd session) the same number of times, and for each gender. As in (Evans 2015, Brewer 2016, Brewer 2019), all participants will receive a follow-up phone call assessment after 3 months of the last session to evaluate the longer-term effect of exposure to the HWLs in real-world setting including HWLs recall, social interactions about WP harms (talk about HWLs with family/friends), and behavioral adaptations in response to exposure to HWLs (e.g., harm perception, quit intention, quitting).*

Such an approach allows:

- 1- Thorough comparisons without the need for large samples using powerful within-between subjects design.
- 2- Comparative testing for HWLs with current practice (no label control).
- 3- Comparative assessment of the 4 HWLs, and the themes they represent, on important

outcomes through between-subjects pre-post analysis.

4- Assessment of the expected effect of HWLs on WP smokers at different stages of their smoking trajectory.

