Inclusion Criteria. Participants need to be generally healthy (at a screening physical examination), between the ages of 21-35 years, willing to provide written informed consent, attend the lab as required, abstain from WP or any tobacco/nicotine for ≥ 12 h prior to study verified by expired air carbon monoxide eCO<5 ppm (Ben Taleb 2018), and use a WP to smoke tobacco in the lab according to study protocol. The 12 hour abstinence period is needed to clear plasma nicotine from prior-to-study smoking (6-8 h after cessation is needed to clear plasma nicotine) (Benowitz 2009) and ensure that all study measures are influenced mainly by study conditions. *Self-reported WP use will be used to define 2 groups of WP smokers (beginners, established), which mostly reflects smokers at different stages of their WP use trajectory ([name] 2016). These are consistent with common WP use patterns among young people in the US, and our previous lab studies with WP smokers, which will enhance recruitment and generalizability of our results (Primack 2013, Haider 2015).*

Exclusion Criteria. As is standard for clinical lab studies involving smoking, safety concerns require that individuals with self-reported history of chronic disease, psychiatric conditions, history of cardiovascular disease, low or high blood pressure (BP) (systolic BP>150 mm Hg, or diastolic BP>100 mm Hg), seizures, or regular use of prescription medications (other than vitamins or birth control) be excluded (Ben Taleb 2018). Women will be excluded if they are breast-feeding or test positive for pregnancy (by urinalysis) at screening. Individuals who fail the eCO test may be rescheduled at another date.

Sample Size. We built our calculation of the sample size for this study on eCO differences in our HWL pilot study (pls. see preliminary studies C.1.2. and Figure 6), which reported a small-

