to-medium effect size (Cohen's $f=0.19$) depending on HWL condition ([name] 2019, b). *This study will include 248 WP smokers (124 beginners; 124 established) randomized to 4 groups (62 each) along the 4 tested HWLs. Using repeated measures ANOVA F test with 2 within and 2 between factors, a total sample size of 240 participants will have at least 80% power to detect small-to-medium size effect (Cohen's $f=0.2$) or larger for $2 \times 2 \times 2 \times 4$ within-subject (H WL condition and time) and between-subject (smoking frequency and 4 different HWLs) effects, as well as their interactions at 0.05 level of significance, assuming sphericity and a moderate correlation (0.5) among repeated measures (Cohen 1988). The proposed sample size will provide sufficient power to detect small to medium effects expected based on our pilot data ([name] 2019, b). It is also feasible as we have not encountered any difficulty in recruiting a large number of WP smokers in our lab studies ([name] 2019, a).*

Screening, Informed Consent. Individuals who are identified as potentially eligible based on the phone screening will be asked to attend an onsite-screening, which will involve assessment of inclusion/exclusion criteria, physical examination, and urine pregnancy testing for women. Prior to screening, potential participants will undergo a review of the study and consent procedures to ensure that they understand the study, its risks/benefits, and their rights as research participants. Consented (written) individuals will then undergo a physical examination conducted by the research nurse, who will have access to an on-call Medical Monitor (physician) in case of concern or for consultation at any point of the study as it is the standard practice in our lab ([name] 2019, a, [name] 2019, b). The physical examination will include measuring BP, heart rate, temperature, pulse oximetry, and weight/height. Successfully consented/screened participants will be scheduled for their 1st session and asked to abstain from all tobacco use 12 hours prior to it.

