Experimental Methods. Participants will be randomly assigned to one of the 4 HWLs conditions and attend the lab for two, ~2-h sessions, separated by a 48-h washout period, and differ by HWL on the device (H WL vs. no-HWL control). Session order will be randomly counterbalanced to avoid order effects; counterbalancing also will allow us to study the effect of HWL on smoking behavior prospectively (i.e. between sessions difference is expected to be less when the HWL condition is tested first). They will also be balanced across the 4 HWLs (62 sessions for each HWL) to allow for equal numbers and robust comparisons of the 4 HWLs and their representative themes.

At the beginning of the 1st session, participants will provide demographic and personal information including age, socioeconomic status, race/ethnicity, and detailed tobacco use history, especially WP use. Then abstinence will be verified by eCO<5 ppm. Those who have eCO>5 ppm will be rescheduled. Those who are abstinent will get familiarized with the study procedures, measures, and they will be given time to adapt to the lab.

After adaptation, continuous measurement of physiological responses begins, and 10 ml of venous blood is sampled, and participants are asked to respond to subjective measures (pls. see below Outcome Measures). They will then begin a maximum 45 min WP smoking session (time recorded) using a device fitted with the pre-selected HWL or no-HWL according to condition. The HWL will be placed in a constant location/size on the device, which will be placed in front of participant seat (at vision level). For each participant, preferred brand/flavor of WP tobacco (verified at screening) will be used to neutralize the effect of nicotine/flavor on study outcomes. We will follow our tested lab protocol developed to study the WP (Ben Taleb 2018), where prior to each session, the lab staff will pack the WP head with 15 g of the participant's favorite tobacco preparation and cover it with perforated foil. Tobacco will be heated with quick-light charcoal disks (33 mm diameter; 6.2 g; Three Kings, Holland, or similar brand). Initially, a single charcoal disk will be used, and several (pre-weighed) ½ charcoal disks will be made available to the participants so they can add *ad libitum* (Cobb 2012). The timing of each

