5. Change in WP smoking will be asked at 3-month assessment using 3 items; “*Since you started the study, 1- did you stop smoking for 1 day or longer because you were trying to quit WP smoking?, 2- did you avoid smoking WP because you were thinking about the HWLs?, and 3- did you stop WP smoking completely because of the HWLs?*” (Brewer 2016).
6. Toxicant exposure includes eCO, plasma nicotine, and EBC oxidative stress.
 - eCo will be measured initially at the beginning of the smoking session (abstinence verification), and within 10 min after the WP smoking session via e-CO monitor (Vitalograph, Lenexa, KS).
 - Plasma nicotine will be assessed pre-/post-smoking. The research nurse will draw Blood samples (~ 10 ml) via a butterfly needle from a forearm vein before smoking session onset and within 10 minutes of its end. Research staff will centrifuge blood samples and freeze plasma immediately, to be analyzed later by Forensic Chemistry Lab at FIU using Liquid Chromatography Mass Spectrometry.
 - Exhaled Breath Condensate (EBC) will be collected pre-post smoking session to test for markers of oxidative stress and DNA damage. We will test for 6 biomarkers (8-oxodGuo, 8-oxoGuo, 8-isoprostanate, formaldehyde, acetaldehyd and malondialdehyde) (Gong 2013, Hu 2015). Samples will be collected during 15 min of tidal breathing through a single-use disposable RTube TM collector (Respiratory Research, Inc., Charlottesville, Va., USA). After sample collection, a plunger will be used to pool the condensed material within the tube into a single sample (about 1.0-2 ml). EBC samples will be divided in aliquots and stored at -80°C. EBC samples will be analyzed by our Forensic Chemistry Lab at FIU using Online Solid-Phase Extraction and Liquid Chromatography Triple Quadrupole Mass Spectrometry (LC-QqQ-MS) and Gas Chromatography Mass Spectrometry (GC-MS) (Hu et al., 2015; Gong et al., 2013). malondialdehyde) (Gong 2013, Hu 2015).

7. Puff topography will be assessed continuously during smoking. It will be measured with a device that was developed by Shihadeh (Shihadeh 2005b), and validated in several WP studies ([name] 2009, Cobb 2015). Briefly, a pressure transducer is integrated into the WP hose, and inhalation-induced pressure changes are amplified, digitized, and sampled at a rate of 1000 Hz. The software converts signals to airflow (ml/sec) and integrates the flow data, producing measures of puff volume, duration, number, and interpuff interval (IPI).

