Statistical Analysis. Prior to analysis, physiological data will be averaged to produce a single baseline value for each measure (10 minutes prior to WP use) and for each 10- minute that a participant was actually using the WP. Topography data will be processed automatically by the topography instrument software to eliminate closely spaced puffs (i.e., IPIs < 300 msec). Such puffs are assumed to be part of the previous puff and the recorded volume and duration values will be added to that preceding puff ([name] 2009). After this procedure, any puffs less than 5 ml will be considered an artifact and automatically discarded. Remaining data will be averaged for each participant in each condition using all remaining values for puff volume, duration, number, and IPI (Shihadeh 2004). We will address the issue of stability of WP puff topography by correlating topography values across sessions (Shihadeh 2005a). For plasma nicotine, values below the limit of quantitation (LOQ) will be replaced with the value of the LOQ ([name] 2011). Demographical data will be examined to determine if there are significant between-group differences on measures that may be related to study outcome (some differences are expected due to design such as past 30-day WP use) though these are expected to be minimized as a virtue of randomization. Unexpected between-group differences will be considered as potential adjustment covariates in the primary analysis (Evans 2006). *The primary analysis of each outcome will involve a 4-factor analysis of variance (or covariance) with two within-subject factors; HWL (HWL vs. no-HWL/control) and time (pre-post smoking), and two between-subject factors; smoking frequency (beginner vs. established WP smokers) and HWL (4 group assignment). This approach will be extended into mixed-effects linear regression model in order to adjust for potential confounders such as gender, education, race, SES, and self-efficacy. To assess if gender has any effect on the results, it will be considered as a covariate and we will test the pre-planned interaction with it to determine heterogeneity of HWL by gender as well as potential differential effects.* We will test for carry over effect statistically and will control for it when testing for the primary factors (Senn 2002). Significance levels will be adjusted for violations of the sphericity assumption using Huynh-Feldt corrections (Keppel 1991). The mean square error terms for the overall interaction will be used to conduct Tukey's honestly significant difference test (Keppel 1991), with comparisons at $P < 0.05$ considered significant.

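### For eCO, the single error term named for Tukey's test is about half the correct variance if post-smoking values are compared; the effect is minor, confined to the post-hoc step, and depends on an unstated comparison family

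*Combined protocol and SAP*

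**What the plan says.** The primary analysis of each outcome (C.5, Statistical Analysis) is a four-factor ANOVA. Label condition (HWL or no HWL) and time (pre or post smoking) are within-subject; smoking frequency and the four assigned labels are between-subject. The post-hoc rule is: "The mean square error terms for the overall interaction will be used to conduct" Tukey's honestly significant difference test, at P < 0.05. The section does not list the means to be compared, the size of the Tukey family, or whether comparisons follow only a significant F test. The stated variance safeguard is: "Significance levels will be adjusted for violations of the sphericity assumption using Huynh-Feldt corrections". The power statement was made "assuming sphericity and a moderate correlation (0.5) among repeated measures".

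For eCO, Outcome Measures says: "eCo will be measured initially at the beginning of the smoking session (abstinence verification), and within 10 min after the WP smoking session". The pre-smoking value is therefore the eligibility check. Experimental Methods states "Then abstinence will be verified by eCO<5 ppm", reschedules anyone above 5 ppm, and applies the same procedure in the second session. The pilot (C.1.2) found "lower levels of eCO following smoking the WP fitted with HWL (17.8 ppm) compared with smoking WP without HWL (24.5 ppm"), and Sample Size says: "We built our calculation of the sample size for this study on eCO differences in our HWL pilot study". Design and Setting describes comparing the four labels on "outcomes through between-subjects pre-post analysis".

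**The concern.** With two two-level within-subject factors, the natural reading of the named term is the HWL × time × subject mean square. It pools the variability of the HWL-minus-no-HWL difference before smoking with that after smoking. If the two are alike, the pooled term serves any within-person comparison. If one is held near zero by an entry rule, the pooled term is too small for comparisons made after smoking and too large for those made before.

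Post-smoking eCO with and without a label is the result the pilot reported, and the pilot's eCO differences drove the sample size. Someone applying the rule could easily run that comparison, or rank the four labels on it. The stake is false post-hoc differences on eCO and intervals that are too narrow.

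**Working it through.** **Plan's own figure.** For the between-subject effect with 8 groups, 4 readings, f = 0.2, correlation 0.5 and N = 240, the noncentrality is 240 × 0.04 × 4 / (1 + 3 × 0.5) = 15.36 and power is 81.8%. Within-subject and interaction effects exceed 99%. The stated 80% or more reproduces and is not in question.

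**Inputs.**
- 248 participants in 8 cells of 31, so 240 error df.
- Pre-smoking eCO confined to 0-5 ppm, so its variance is at most (5/2)² = 6.25 ppm². A uniform distribution, assumed below, gives 25/12 = 2.08 ppm².
- Pilot post-smoking difference 24.5 − 17.8 = 6.7 ppm, n = 30, f = 0.19.
- No SD is stated. If f = d/2, the SD is 6.7 / (2 × 0.19) = 17.6 ppm. If the pilot P < 0.05 came from a paired t test, the SD of the paired difference is below 6.7 × √30 / 2.045 = 17.9 ppm. The range 5-17.6 ppm is used.
- Correlation 0.5, as in the power statement. The variance of the paired post-smoking difference, Vd, is then 2 × SD² × (1 − 0.5) = SD².

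**Error term.** With pre-smoking readings uncorrelated across sessions and with post-smoking ones, MSE = (Vd + 2·Vpre)/4. Tukey's test uses 2·MSE as the variance of a paired difference; the correct value is Vd. So

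ratio = (Vd + 2·Vpre) / (2·Vd), which tends to 0.5 as Vpre tends to 0.

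At SD 17.6: (309.8 + 4.2)/(2 × 309.8) = 0.507. At SD 5: (25 + 4.2)/(2 × 25) = 0.583.

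**Actual error when nothing differs.** The critical values q(0.95; 2, 4, 32 means; 240 df) are 2.786, 3.659 and 5.414. The pair error is 2·P(t240 > (q/√2)·√ratio). For four labels it is P(studentized range of 4 > 3.659·√ratio).

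| Post SD (ppm) | Ratio | HWL vs no-HWL, 2 means | Same pair, 4 cells | Same pair, 32 cells | Four labels on post-smoking difference |
|---|---|---|---|---|---|
| 5 | 0.583 | 13% | 5% | 0.4% | 20% |
| 8.8 | 0.527 | 15% | 6% | 0.6% | 24% |
| 17.6 | 0.507 | 16% | 7% | 0.7% | 26% |

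Simulation of the full layout agrees. In the four-cell family the pre-smoking pair is almost never declared and smoking truly raises eCO, so the family-wise error is about 5-7%.

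**Sensitivity.** At the limiting ratio of 0.5 the two-mean and label errors are 16.5% and 26.2%. With the largest pre-smoking variance the cap allows (6.25), they are 9% and 12% at SD 5, and 16% and 25% at 17.9. If the HWL-minus-no-HWL differences before and after smoking correlate between −0.5 and +0.5 (post SD 17.6, pre SD 1.14), the two-mean error is 15-18%.

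**What is sound.** The HWL × time F test stays at about 5%, as do label comparisons on pre-post change relative to control. With each contrast's own error variance, every comparison returns to about 5%.

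**Huynh-Feldt.** Each within-subject factor has two levels, so epsilon is 1 and nothing is corrected. The correction acts on F-test df, not on the mean square that Tukey's test uses.

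**The case against.** The strongest reply is that the plan never says it will compare post-smoking eCO. Its objectives speak of pre-post change under two conditions, and its label comparison is also framed as pre-post; for such contrasts relative to control the named term is adequate. This stands: the problem is conditional on how the rule is applied.

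Second, an interaction suggests at least the four HWL × time cells, where family-wise error is only about 5-7%. This also stands. Tukey's test controls the family rate, so holding the single pair to a 1% benchmark would overstate the fault.

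Third, a valid test is already primary. With equal pre-smoking means, the HWL × time F test addresses essentially the same null as the post-smoking contrast. A gate on that test would hold HWL versus no-HWL at 4.8-5.0%. The plan states no gate, but it does not exclude one.

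A reader might go further and cite the 78-82% chance of some false difference among the 16 post-smoking cells of a 32-cell test. The documents do not support laying that on the eCO cap. The plan states no such test, and the rate would be 29% even with equal variances, because the term omits between-person variation.

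The rule as written still supplies one error term for every comparison, and nothing in the section limits it to contrasts for which that term is right.

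**Conclusion.** The concern holds in limited form and is minor. For eCO, the named term is about half the correct variance for HWL versus no-HWL after smoking, unless the post-smoking spread is very small. The condition that fails is similarity of the paired HWL-minus-no-HWL difference's variance before and after smoking, with their covariance also playing a part; equal variance of the raw readings is not quite the criterion.

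The consequence turns on the unstated family. It ranges from about 13-16% (two means), through about 5-7% family-wise (four cells), to conservative for that pair (32 cells). It is about 20-26% if four labels are ranked on the post-smoking difference. All this assumes the interaction reading of the term, the inferred SD range, uniform pre-smoking values, correlation 0.5 and no gate.

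A reader might infer that Tukey comparisons of eCO generally lose their 5% level, or that the trial's main conclusions are at risk. Neither follows: interaction contrasts are sound, and the omnibus F tests, both hypotheses and the power calculation are untouched.

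**What to change.** Replace the post-hoc sentence with wording such as:

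> Pairwise comparisons will be pre-specified contrasts, each with its own standard error and degrees of freedom, from a mixed model with unstructured covariance across the repeated readings (or from per-person contrast scores). They include HWL versus no-HWL after smoking, and the six label pairs on the HWL-minus-no-HWL effect, Tukey-adjusted over those six pairs.

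State also whether comparisons are made only after a significant F test. For the sensory (DSQ) and evaluation (WES) scales and puff topography, which have no pre-smoking reading, use the session value. For label pairs on pre-post change relative to control the present term is already adequate; the new wording only fixes the family.

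The cost is SAP wording and, for HWL versus no-HWL on post-smoking eCO, wider intervals. Against a two-mean rule the factor is 1/√ratio: 1.31 at SD 5, 1.38 at 8.8 and 1.40 at 17.6. Against a four-cell family it is (2.786/3.659)/√ratio, or about 1.05-1.07 at SD 8.8-17.6 and no change at SD 5. Against 32 cells the intervals become narrower, at about 0.71-0.72 times (SD 8.8-17.6).

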Waterpipe (WP) smoking has become one of the leading tobacco use methods among youth in Florida. The impact of this dramatic rise is amplified by the mounting evidence of WP addictive and harmful nature, as well as the lag of policy response to it. Evidence suggests WP use leads to nicotine addiction, and increases the risk of lung cancer, heart and respiratory disease and exposure to secondhand smoke. The spread of WP use among youth has been fueled by a misperception of reduced-harm compared to cigarettes. Health Warning Labels (HWLs) represent one of the most successful tobacco control strategies to communicate smoking-related risks, and studies have consistently shown that HWLs are associated with a decrease in smoking rates and smoking-related morbidity and mortality. Therefore, communicating WP risks to young people through HWLs has been identified as a priority by major health bodies in the US including the FDA.

Using the Delphi method among international tobacco control experts, our team has developed a set of 12 WP HWLs corresponding to 4 health themes; health risks/addiction, harm to others, WP-specific harm, WP harm compared to cigarettes. Building on this work, and using a mixed-method approach incorporating qualitative and quantitative research, we propose to:

Aim 1: Adapt the 12 HWLs to young WP smokers in Florida using exploratory focus groups.

Aim 2: Test in a clinical lab experiment the performance of the top 4 HWLs on the WP device compared to no-HWL/control on harm perception, intention to quit, and toxicant exposure (CO, nicotine, oxidative stress).

Aim 3: Use the knowledge obtained to advocate for the adoption of WP-HWLs policies and disseminate information about WP harmful effects to young people in Florida and nationally.

Communicating WP risks through HWLs promises to reduce WP use and WP-related morbidity and mortality among young adults in Florida. This pioneering work will inform the FDA and public health advocates on the potential of WP-HWLs policies and provide a model for other states to respond to the WP epidemic.

Health Impact: (3,464/3,500) characters

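### The 80% power is for ANOVA F tests; the only rule for single comparisons is Tukey's HSD over an unstated set of means, with no planned label-versus-no-label contrasts and no power given for them

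*Combined protocol and SAP*

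**What the plan says.** C.5, Sample Size, names the test: "Using repeated measures ANOVA F test with 2 within and 2 between factors". The power claim made for that test is that "a total sample size of 240 participants will have at least 80% power to detect small-to-medium size effect (Cohen's $f=0.2$) or larger" can be found. The error rate and correlation behind the claim are given as "at 0.05 level of significance, assuming sphericity and a moderate correlation (0.5) among repeated measures". The allocation is "This study will include 248 WP smokers (124 beginners; 124 established) randomized to 4 groups (62 each) along the 4 tested HWLs", so each label-by-frequency group has 31 people. The effect size comes from the pilot's exhaled CO result, described as small- "to-medium effect size (Cohen's $f=0.19$) depending on HWL condition"; the pilot SD is not given.

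C.5, Statistical Analysis, makes a four-factor ANOVA or ANCOVA the primary analysis of each outcome. For single comparisons it says: "The mean square error terms for the overall interaction will be used to conduct Tukey's honestly significant difference test", with P < 0.05 counted as significant. That names an error term. It does not say which means are compared.

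The Scientific Abstract words Aim 2 as: "Test in a clinical lab experiment the performance of the top 4 HWLs on the WP device compared to no-HWL/control". C.5, Experimental Methods, balances 62 sessions per label so that the four labels can be compared. The Impact paragraph after Statistical Analysis promises tested labels for dissemination. The hypotheses in C.5, Objectives and Hypotheses, are about HWL versus no-HWL overall and a larger effect in beginners.

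**The concern.** A significant pooled HWL effect does not show which labels worked, and the plan means to disseminate particular labels. That conclusion needs each label to be compared with its own no-label session, and the plan neither names this comparison nor gives its power. The only available rule is Tukey's HSD, which controls error over every pair in whatever set of means it is given.

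The full design has 2 x 2 x 2 x 4 = 32 cells and 32 x 31 / 2 = 496 pairs. Only 8 of these compare post-smoking HWL with post-smoking no-HWL in the same people. After averaging over smoking frequency there are 16 cells and 120 pairs, of which 4 are the wanted ones. The remainder includes pairs such as pre-smoking established smokers under one label against post-smoking beginners under another. Such pairs answer no trial question but still raise the critical value.

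Two things are at stake. A label with a real effect of the planned size may well be reported as not different from no label. And because the set of means is not fixed, it could be chosen after the data are seen.

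**Working it through.** **1. The plan's own figure.** For a between-subject effect with 8 groups (2 x 4; 7 numerator df), N=240, f=0.2, m=4 measures and correlation 0.5:

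λ = f²·N·m / (1 + (m−1)ρ) = 0.04 × 240 × 4 / 2.5 = 15.36.

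With F(7, 232), critical value 2.05, power is 81.8%. The other four-measure F tests have 92% or more. The printed 80% is sound for F tests.

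**2. One label against its own no-label session.** Inputs from the documents: n=62 per label (31 per label and frequency group), f=0.19 (pilot) or 0.20 (planning), ρ=0.5, error df = 248 − 8 = 240. Assumptions added here: equal variances, and a gap only at the post-smoking HWL value, of size d = 2f = 0.38-0.40 SD. The documents do not say how f maps to a pairwise gap.

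ncp = d·√n / √(2(1−ρ)). For n=62 this is 0.38 × 7.874 = 2.99 to 0.40 × 7.874 = 3.15. For n=31 it is 2.12 to 2.23.

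Critical values are t for the planned contrasts and q(0.95; k, 240)/√2 for Tukey over k means:

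| Rule | Critical value | n | Power |
|---|---|---|---|
| Planned contrast, unadjusted | 1.97 | 62 | 85-88% |
| Planned contrasts, Bonferroni over 4 | 2.52 | 62 | 68-74% |
| Tukey, 8 post-smoking means (label x condition) | 3.06 | 62 | 48-54% |
| Tukey, 16 means (condition x time x label) | 3.46 | 62 | 32-38% |
| Tukey, 32 cells (one label in one frequency group) | 3.83 | 31 | 5-6% |

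A simulation of the full design (4,000 trials) at d=0.38 gave 84.6%, 68.5%, 47.5%, 32.3% and 4.6% for these rows.

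The last row is not comparable with the others. It concerns one label within one frequency group, and with n=31 even an unadjusted contrast has only 56-60%.

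**3. The pooled test.** The same simulation gave the HWL x time F test 98.6% power at d=0.38 and 99.4% at d=0.40.

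**4. Sensitivity of the Tukey figures.**
- Correlation, 8 means: 30-35% at ρ=0.3 and 79-84% at ρ=0.7.
- Effect-size mapping: if f=0.2 describes the HWL main effect or the HWL x time effect and there is no pre-smoking difference, the post-smoking gap is 4f = 0.8 SD. At ρ=0.5, power is then 73% (32 cells) to over 99% (8 or 16 means with n=62).
- Eight means that average pre- and post-smoking values: 92% at d=0.40 if the gap is present at both times, 21% if it is present only after smoking.

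**5. Which planned contrast.** Under equal variances and equal correlation, a raw pre-to-post change contrast has variance 4(1−ρ) = 2 instead of 2(1−ρ) = 1. Its ncp falls to 2.12-2.23, so power is 56-60% unadjusted and 35-39% with Bonferroni over 4, hardly better than Tukey over 16 means. Adjusting the post-smoking contrast for the pre-smoking difference does not carry this penalty: the covariance of the two differences is ρ − ρ − ρ + ρ = 0, so the 68-74% is essentially kept.

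**The case against.** The strongest reply is that the plan never says Tukey will run over 8, 16 or 32 cells. It names an error term, so any all-pairs power figure rests on an inferred set of means. This stands, and the figures above are therefore conditional. It also describes the gap, since an unstated set of means lets power range from about 54% to 32% for a label as a whole on the same assumptions.

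Second, the hypotheses are about HWL versus no-HWL overall and about beginners versus established smokers, and both are tested by F tests. This stands too. The label-specific question comes from the wording of Aim 2 and the promise of tested labels, not from a numbered hypothesis.

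Third, the planned contrasts also miss 80%: 68-74% with Bonferroni. The chance that all four working labels are shown to work is only about 0.683⁴ = 22% to 0.736⁴ = 29%, treating the four as independent. That is true, and is a reason to print the power rather than to keep the weaker rule. Holm is never less powerful than Bonferroni.

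A reader might also infer three stronger things that the documents do not support. One is that the 80% is wrong; it reproduces, and it is never claimed for pairwise tests. Another is that a given label has only about 5% power; that figure is for one frequency group of 31. The third is that every Tukey reading falls well short of 80%; step 4 shows readings of 84%, 92% and over 99%.

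**Conclusion.** The point holds as a gap in the analysis plan, not as an error in the sample size. The plan gives no planned label-versus-no-label contrasts, no defined set of means for Tukey's HSD, and no power for label-specific conclusions. If Tukey is applied to all pairs of 16 or 8 interaction means, power for one label is about 32-54%, against 68-74% for four planned contrasts with Bonferroni. This assumes a post-smoking gap of 0.38-0.40 SD, correlation 0.5, equal variances and 62 complete participants per label. A lower correlation makes it worse; a higher correlation or a 0.8 SD gap can remove the shortfall. The pooled HWL conclusion is not at risk. The change is worth making because it is cheap and settles in advance how each label will be judged.

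**What to change.** In C.5, Statistical Analysis, replace all-pairs Tukey on interaction cells with:

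1. Four planned within-person contrasts, each label against its own no-label session, on the post-smoking value. Adjust for pre-smoking values where they are collected, rather than using a raw change score. Outcomes measured only after smoking (DSQ, WES) use the post-smoking value alone. Apply Holm over the four.
2. Tukey's HSD only for the six pairwise comparisons among the four labels, applied to each person's HWL minus no-HWL difference.

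In C.5, Sample Size, state that the 80% refers to the ANOVA F tests. Add the power of the label-specific contrasts under the rule actually used, with the assumed gap and correlation, even where it is below 80%.

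The cost is plan wording; no participants or data are added. The downside is that other cell-by-cell comparisons become exploratory.
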